### **7.2 Collection and Derivation of Efficacy Assessments**

On a daily basis during the 28-day baseline period and throughout the study, participants are to record into an eDiary information on the daily total duration of headache, headache specific characteristics and symptoms, the worst pain severity, and use of any acute headache pain medication. Participants will be able to report headache data, including absence of headache, for the day of the eDiary report and for the day immediately prior to the day of the eDiary report, as long as information reported is for a time subsequent to the participant's most recent report. This is defined as a one-day "missing-recall" window.

Following randomization on Day 1, there are 4 visits at 2-week intervals, followed by 2 visits at 4-week intervals; altogether encompassing a 12-week double-blind treatment phase of the study and a 4-week follow-up phase. In practice, there may or may not be exact 2-week or 4-week durations between two consecutive visits and the visits might not align with each

28-day period recorded in the eDiary (ie, Weeks 1 to 4, 5 to 8 and 9 to 12, corresponding to Days 1 to 28, 29 to 56, and 57 to 84). Therefore, for data analysis purposes, the number of migraine days during the last 28 days prior to the randomization date, will serve as the “baseline”, and change from baseline will be calculated for consecutive 28-day periods beginning with the date of first dose of study intervention.

In order to be randomized, a participant should be in the baseline phase for at least 28 days and must report eDiary data for at least 20 days (including missing recall) during the 28-day baseline period. If less than 28 days of baseline data are reported, the number of headache days and other such counting variables for “baseline” will be prorated to standardize the count to a 28-day equivalent. Subsequent to treatment start, the number of headache days will be counted in successive and non-overlapping 4-week (ie, 28-day) windows. Headaches that continue into a subsequent 4-week period will be counted (with recorded severity and duration) as occurring in each period.

If any postbaseline eDiary window for a participant has at least 14 but less than 28 days of reported data, the prorated approach will be used. If a participant reports less than 14 days of headache data, the participant’s observed counts in that particular 28-day eDiary window will be set to missing for that window. These prorating rules will be applied to all efficacy analyses of eDiary data unless otherwise stated.

### **7.2.1 Primary Efficacy Variable**

The primary efficacy variable is the change from baseline in mean monthly migraine days across the 12-week treatment period. Baseline is defined as the number of migraine days during the last 28 days of the baseline phase, ie, Day –28 to –1.

[figure not shown]
### **7.2.2 Secondary Efficacy Variables**

The secondary efficacy variables for the United States and the EU:

[figure not shown]
- Change from baseline in mean monthly headache days across the 12-week treatment period.
- Change from baseline in mean monthly acute medication use days across the 12-week treatment period.
- At least a 50% reduction in 3-month average of monthly migraine days.

- Change from baseline in MSQ v2.1 Role Function-Restrictive domain score at Week 12
- Change from baseline in mean monthly Performance of Daily Activities domain score of the AIM-D across the 12-week treatment period.
- Change from baseline in mean monthly Physical Impairment domain score of the AIM-D across the 12-week treatment period.

### 7.2.3 Additional Efficacy Variables

Approval Date: 15-May-2020 16:33:54 (GMT)

Approval Date: 15-May-2020 16:33:54 (GMT)

### 7.3 Hypothesis and Methods of Analysis

For efficacy analyses, data will be analyzed according to participants' randomization assignments, regardless of actual treatment received.

For safety data analyses, the participants will be analyzed according to actual treatment received (rather than as randomized).

#### 7.3.1 Primary Efficacy Analyses

The primary efficacy endpoint is the change from baseline in mean monthly migraine days across the 12-week treatment period. The primary null hypothesis is that atogepant treatment doses (atogepant 10 mg, atogepant 30 mg, and atogepant 60 mg once a day) are each equally effective to placebo in mean change from baseline in mean monthly migraine days across the 12-week treatment period. The alternative hypothesis is that at least 1 of the 3 doses of atogepant has a different effect than placebo.

The primary comparison between treatment groups will be done by a mixed-effects model for repeated measures (MMRM) of the change from baseline. The statistical model will include treatment group, visit, prior exposure (yes/no) to a migraine prevention medication with proven efficacy, and treatment group by visit interaction as categorical fixed effects. It will also include the baseline score and baseline-by-visit interaction as covariates. An unstructured covariance matrix will be used to model the covariance of within-participant repeated measurements. The Kenward-Roger approximation ([Kenward 1997](#)) will be used to estimate the denominator degrees of freedom. The analysis will be performed based on all postbaseline values using only the observed cases without imputation of missing values. Pairwise contrasts in the MMRM model will be used to make the pairwise comparisons of each atogepant dose to placebo.

Only data collected during the double-blind period will be included in the analysis. Participants are always analyzed based on the treatment group assigned by randomization.

### **7.3.1.1 Sensitivity Analyses in Missing Data Handling**

Multiple sensitivity analyses for missing data handling will be conducted and are summarized below. Details of the sensitivity analyses will be provided in the statistical analysis plan.

#### **ANCOVA Model Based on 3-month Average of the Monthly Migraine Days**

The response variable for the ANCOVA model is the change from baseline in 3-month average of monthly migraine days for each participant. The ANCOVA model includes terms for treatment, prior exposure (yes/no) to a migraine prevention medication with proven efficacy, and baseline score. The treatment difference for atogepant doses versus placebo will be estimated and reported along with the corresponding 95% CI and nominal p-value for superiority testing. This analysis is also termed as “supportive analysis”.

#### **Within-group Imputation Based on Observed Data**

A sensitivity analysis will be performed based on imputation using participants from the same treatment group with observed data under the MAR assumption. Missing data for participants who prematurely discontinued are assumed to copy the profile of participants in the same treatment group with observed data.

#### **Copy-reference Approach**

The Copy-reference Approach will be performed on the primary endpoint to assess the robustness of the MMRM analysis to possible violation of the missing-at-random (MAR) assumption. This sensitivity analysis is one type of pattern-mixture models (PMM), under which data could be missing-not-at-random (MNAR), with repeated analyses combined via the reference based multiple imputation (MI) procedure. Participants who discontinued in the Atogepant groups are assumed to have no treatment effect after the discontinuation. Participants are assumed to copy the profile of placebo arm and missing values are imputed based on the distribution estimated from the placebo group under the MAR using copy-reference approach.

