#### **7.4.5 Population-level Summary**

The population-level summary for the primary endpoint is the difference in primary variable means between each atogepant group and placebo.

Participants are always analyzed based on their treatment assignment by randomization. To obtain the estimate of treatment effect defined in the off-treatment hypothetical estimand, a MMRM similar to the primary analysis specified in Section 7.3.1 will be performed on observed data including both on-treatment and off-treatment monthly migraine days.

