## 8.8 Early Discontinuation of Participants

A premature discontinuation will occur when a participant who signed the ICF and has been randomized ceases participation in the study, regardless of circumstances, before completion of the study. Participants can be prematurely discontinued from the study for one of the following reasons:

- AE
- Lack of efficacy
- Lost to follow-up
- Non-compliance with study intervention
- Other
- Pregnancy
- Protocol deviation
- Site terminated by Allergan
- Study terminated by Allergan
- Withdrawal by participant

Participants may voluntarily withdraw from the study at any time. Notification of early participant discontinuation from the study and the reason for discontinuation will be made to Allergan and will be documented on the appropriate case report form. All randomized participants who prematurely discontinue from the study, regardless of cause, should be seen for final study assessments. The final assessments will be defined as completion of the evaluations scheduled for Visit 7/ET and Visit 8 Follow-up, 4 weeks post the last dose of study intervention. These participants must continue to complete their eDiary through Visit 8 Follow-up.

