10.2.1 Primary Analysis

The endpoint will be analyzed using a mixed model for repeated measures (MMRM). The response variable is the change from baseline to each postbaseline month in monthly migraine days. The model will include treatment group, visit (derived as month), prior exposure (yes/no) to a migraine prevention medication with proven efficacy, and treatment group by visit interaction as categorical fixed effects. It will also include the baseline score and baseline-byvisit interaction as covariates. The stratum "prior exposure (Yes/No)" will use the actual stratification factor from prior medication collected by eCRF. The analysis will be performed based on evaluable postbaseline data using only the observed cases without missing data imputation. Only data collected during the double-blind period will be included in the analysis. Participants are always analyzed based on the treatment group assigned by randomization.

Restricted maximum likelihood method will be used. The within-patient correlation will be modeled using the unstructured covariance matrix. If the model does not converge, then the Toeplitz covariance structure will be used. if the model with the Toeplitz covariance structure does not converge, then the compound symmetry covariance structure will be used. The Kenward-Roger approximation will be used to estimate denominator degrees of freedom. Contrasts will be constructed to obtain the average treatment effects across the 12-week treatment period to compare each atogepant treatment group versus the placebo group. Each

Allergan SAP 31	01-301-002 AGN-241689
treatment effect and treatment comparisons will be estimated by the LS	Means and their
differences in LS Means, along with their SE and 95% confidence inter	vals, and the p-value
corresponding to the between-treatment group difference. The sample S	AS code is given as
follows	

[figure not shown]

The impact of dropouts on the primary efficacy measure will be explored graphically by plotting the response profiles by the dropout reason. Plot of mean change from baseline in the number of migraine days versus visit (month) based on the observed cases will be provided in each treatment group by major reason of early termination, such as, adverse events, lack of efficacy, withdrawal of consent, lost to follow-up, etc. Similar plot for completers in each treatment group will be provided as a reference.

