10.5 Off-treatment Hypothetical Estimand

This section defines an estimand

Per study design (Protocol Sections 8.4.3.1 and 8.8), eDiary data will be collected for participants who early terminated from the double-blind treatment period during the 4 weeks between V7 (Early termination visit) and V8 (Follow-up Visit), i.e., participants who prematurely discontinued (before Week 12) will continue to complete eDiary efficacy assessments while offtreatment.

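### Does the protocol misdescribe its copy-reference analysis by saying that discontinued participants have no treatment effect after stopping?

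*Protocol*

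**What the plan says.** Protocol 7.3.1.1 lists several sensitivity analyses for missing data. The copy-reference analysis is the only one in the visible text described as allowing data missing not at random, and its stated purpose is to test the primary MMRM against failure of the missing-at-random assumption. It is described in two steps. First, "Participants who discontinued in the Atogepant groups are assumed to have no treatment effect after the discontinuation". Second, these participants follow the placebo profile, and "missing values are imputed based on the distribution estimated from the placebo group under the MAR using copy-reference approach".

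The section is a summary: "Details of the sensitivity analyses will be provided in the statistical analysis plan". In the public SAP, section 10.2.3 breaks off where the imputation steps would begin, and no copy-reference text can be seen.

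Two other parts of the plan bear on the same question. SAP 10.2.1 states that "The impact of dropouts on the primary efficacy measure will be explored graphically by plotting the response profiles by the dropout reason". Protocol 8.8 requires participants who stop early to keep their diary going until a visit "4 weeks post the last dose of study intervention", and SAP 10.5 confirms that "participants who prematurely discontinued (before Week 12) will continue to complete eDiary efficacy assessments while offtreatment". Under Protocol 7.4.5, an MMRM similar to the primary one "will be performed on observed data including both on-treatment and off-treatment monthly migraine days".

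**The concern.** A reader may take the first sentence literally: once a participant stops atogepant, the expected difference from placebo is zero. Copy-reference imputation need not do that. It draws the missing months from the placebo model given what was observed for that participant. Someone who ran below the placebo mean on drug is then imputed below the placebo mean afterwards, to a degree set by the correlation between months. The sentence does not itself say whether the imputation conditions on the participant's own months.

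At stake is how severe this stress test is taken to be. Its result could be reported as robustness to complete loss of benefit at discontinuation when, with correlated months and good responders among those who stop, the method applies only part of that penalty.

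**Working it through.** **The plan's own figure.** Inputs from Protocol 7.6: 218 per arm, difference 1.5 days, SD 3.5, two-sided alpha 0.0167. Standard error = 3.5 × √(2/218) = 0.335, noncentrality = 1.5/0.335 = 4.47, 434 degrees of freedom. Power is 98.1%, matching the stated 98%. The copy-reference text states no figure.

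**Assumptions not in the documents.** Correlation r between months of 0.4 to 0.8, either exchangeable or AR(1). A benefit of 1.5 days in every month. Dropout D of 10% or 20%, split equally after Months 1 and 2. A share f of the average benefit enjoyed on drug by those who later stop (0, 0.5 or 1).

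**Carry-over weight.** The expected imputed difference from placebo is w × f × 1.5, where w comes from regressing later months on observed months in the placebo covariance.

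- Exchangeable: w = r after one observed month and 2r/(1+r) after two. At r = 0.8 the three imputed months (two for a Month 1 stop, one for a Month 2 stop) have weights 0.80, 0.80 and 0.89, mean 0.83.
- AR(1): w = r one month ahead and r² two months ahead. At r = 0.4 the weights are 0.40, 0.16 and 0.40, mean 0.32.
- Conditioning on baseline as well keeps the mean weight within 0.32 to 0.83.

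Example: exchangeable r = 0.5, one month observed, f = 1. The imputed Month 2 difference is 0.5 × 1.5 = 0.75 days in favour of drug. A simulation gave the same value. Literal zero effect gives 0.

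**Effect on the 12-week estimate.** The missing share of arm person-months is (2 × D/2 + D/2)/3 = D/2. The departure from literal zero effect is f × 1.5 × w × D/2.

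| f | D = 10% | D = 20% |
|---|---|---|
| 1 | 0.024–0.062 days | 0.048–0.124 days |
| 0.5 | 0.012–0.031 | 0.024–0.062 |
| 0 | 0 | 0 |

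At f = 1 the full no-effect penalty is 1.5 × D/2 = 0.075 or 0.15 days, and copy-reference applies the fraction 1 − w of it, that is 17% to 68%.

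**Power at D = 20%, f = 1, ignoring imputation variance.** Literal no effect: 1.5 − 0.15 = 1.35 days, 94.7%. Copy-reference: 1.35 + 0.048 = 1.398 to 1.35 + 0.124 = 1.474 days, 96.1% to 97.7%.

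**The obvious alternative.** Jump-to-reference centres on the participant's own arm before stopping, so its imputed difference is w × (f − 1) × 1.5. It equals zero effect only at f = 1. At f = 0.5 it is 0.012 to 0.062 days too pessimistic over the two dropout rates, and at f = 0 it is 0.024 to 0.124 days too pessimistic, which is where copy-reference is exact.

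**Observed off-treatment data.** Dropouts leave 1.5D missing months per participant randomised. Four further weeks of diary fill D of these, or two-thirds. What stays unobserved is 0.5D/3 = D/6 of arm person-months, 1.7% to 3.3%, if diaries are completed.

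**The case for a change.** The best case for a change is that the two sentences, taken one at a time, do not agree, and that the first is what a non-specialist will remember. This is the only analysis labelled as missing not at random in a trial meant to support registration, and when those who stop had average benefit it applies as little as 17% of the penalty the sentence suggests. One clause stating what the imputation conditions on would remove the ambiguity at almost no cost.

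The algebra stands, and so does the remark that the phrase is loose. The step to a needed change does not.

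- Imputing under missing at random from the placebo distribution is naturally read as conditioning on observed values, and the method is named. The plan's two sentences together already carry the meaning that the clause would add.
- The exact conditioning set belongs in the SAP text that cannot be seen, so it cannot be called absent.
- Neither document plans to claim robustness to complete loss of benefit.
- The figures lean high if 10% to 20% is total dropout. Protocol 7.2 prorates and keeps any 28-day window with at least 14 diary days, so a stop after about Day 70 may leave no month missing. Participants with no evaluable double-blind month are outside the mITT population.
- Protocol 8.8 lists "Lack of efficacy" among the reasons for stopping. For those who stop because the drug did little, f is low and the gap shrinks towards zero.

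Adding jump-to-reference would trade one possible error for the opposite one.

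**Conclusion.** No change to the plan is called for. The phrase is imprecise if read alone. Read with the sentence that follows, it means that missing months follow the placebo model given the participant's observed months, with no further drug effect, so benefit seen before stopping may be partly retained when months are correlated. An analyst implementing copy-reference would do the same thing with or without a rewording.

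The gap between phrase and method is at most 0.124 days against 1.5 in the ranges tried, and power stays at 94.7% even under literal zero effect. These sizes rest on assumed correlation, dropout, timing and benefit before stopping, none of which the documents give. The dropout-reason profiles offer descriptive context on how those who stopped had fared, though they are observed means in non-randomised subsets. The off-treatment MMRM brings in observed data for the first four weeks after stopping. The sponsor may add a clarifying clause if the text is being edited anyway, and check that it agrees with the SAP text not visible here; no result or decision rule depends on it.

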## **7. Statistical Procedures**

### **7.1 Analysis Populations**

The ITT population will consist of all randomized participants. All efficacy analyses will be performed using the mITT population, consisting of all randomized participants who received at least 1 dose of study intervention, had an evaluable baseline period of eDiary data and had at least 1 evaluable post-baseline 4-week period (Weeks 1 to 4, 5 to 8, and 9 to 12) of eDiary data during the double-blind treatment period. All safety analyses will be performed using the safety population, consisting of all participants who received at least 1 dose of study intervention.

The primary efficacy analysis population [REDACTED] includes all randomized participants who received at least 1 dose of study treatment, had an evaluable baseline period of eDiary data and had at least 1 evaluable post-baseline 4-week period (Weeks 1 to 4, 5 to 8, 9 to 12) of eDiary data during the double-blind treatment period and follow-up period, regardless of whether on study treatment or off study treatment.

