The Safety Population includes all participants who received at least 1 dose of study intervention. All safety analyses will be performed using the Safety Population and based on the treatment actually received, regardless of assigned treatment according to the planned randomization. Participants will be summarized according to the study treatment received for the majority of treatment period.

The Modified Intent-to-Treat (mITT) Population includes all randomized participants who received at least 1 dose of study intervention, had an evaluable baseline period of eDiary data and had at least 1 evaluable post-baseline 4-week period (Weeks 1 to 4, 5 to 8, and 9 to 12) of eDiary data during the double-blind treatment period. All efficacy analyses described in Sections 10.2 - 10.4 will be performed using the mITT population and based on the randomization assignment, regardless of the actual treatment received. All efficacy analyses will be conducted using mITT population unless specified otherwise.

The analysis population for Off-treatment Hypothetical Estimand includes all randomized participants who received at least 1 dose of study treatment, had an evaluable baseline period of eDiary data and had at least 1 evaluable post-baseline 4-week period (Weeks 1 to 4, 5 to 8, 9 to 12) of eDiary data during the DB treatment period and follow-up period, regardless of whether on study treatment or off study treatment.

7 Participant Disposition

The number of participants in the ITT, Safety, and mITT Populations will be summarized by treatment group; the number of participants screened will be summarized for overall only. The number of participants in the ITT Population will also be summarized by treatment group for the

SAP 3101-301-002 AGN-241689

following factors: 1) Randomization stratification factor (prior exposure [yes/no] to a migraine prevention medication with proven efficacy) from IWRS; 2) Prior exposure to migraine prevention medication with proven efficacy based on prior medication collected from eCRF, which will be termed as "actual strata" in the SAP. The list of participants with incorrect randomization stratum will be provided.

[figure not shown]

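### On the visible text, the copy-reference sensitivity analysis runs in mITT, so participants with no evaluable double-blind month are not imputed in the plan's missing-not-at-random check

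*Protocol*

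**What the plan says.** Protocol 7.3.1.1 lists copy-reference imputation among the missing-data sensitivity analyses. Its purpose is "to assess the robustness of the MMRM analysis to possible violation of the missing-at-random (MAR) assumption". Missing values in the atogepant arms are drawn from the placebo distribution, on the premise that "Participants who discontinued in the Atogepant groups are assumed to have no treatment effect after the discontinuation". No analysis population is named there.

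The population comes from the general rules:

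- Protocol 7.1: "All efficacy analyses will be performed using the mITT population, consisting of all randomized participants who received at least 1 dose of study intervention". Membership also requires an evaluable baseline and that the participant "had at least 1 evaluable post-baseline 4-week period (Weeks 1 to 4, 5 to 8, and 9 to 12) of eDiary data" in the double-blind period.
- SAP Section 6: "All efficacy analyses described in Sections 10.2 - 10.4 will be performed using the mITT population", and then "All efficacy analyses will be conducted using mITT population unless specified otherwise". The missing-data sensitivity analyses are in SAP 10.2.3, inside that range.
- Protocol 7.2 sets the evaluability threshold. "If a participant reports less than 14 days of headache data" in a 28-day window, the count for that window is set to missing.

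Protocol 7.1 also defines a wider set: "The ITT population will consist of all randomized participants". In the visible text this ITT population is used for disposition, not for any efficacy analysis.

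**The concern.** A reference-based imputation asks what happens to the estimate if people who stop the drug lose its benefit. The people with the least observed data depend most on that assumption, and those with no evaluable double-blind month depend on it entirely. Under the mITT rule they are removed before the assumption can be applied to them. The check then covers missingness in the later months of people who supplied at least one month, but not missingness of the whole post-baseline record.

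Whether someone has an evaluable month is settled after randomisation, so the check keeps a post-randomisation exclusion. Under the copy-reference rule, adding the excluded atogepant participants would pull the estimate toward zero in expectation if the drug works. Leaving them out therefore tends to favour the drug. At stake is how complete the stress test is, not the validity of the primary analysis.

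**Working it through.** **Step 1: who is left out.** Copy-reference names no population (Protocol 7.3.1.1), so mITT applies (Protocol 7.1, SAP Section 6). mITT needs one evaluable double-blind month, and a month needs at least 14 reported days (Protocol 7.2). The participants left out for lack of post-baseline data are those with fewer than 14 reported days in each of Weeks 1-4, 5-8 and 9-12. Someone who leaves in week 3 with 14 diary days is in mITT, and their later months are imputed. Never-dosed participants and those without an evaluable baseline are also outside mITT. The exclusion applies to placebo as well.

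**Step 2: what the other planned analyses do for them.**

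- The ANCOVA on the 3-month average (SAP 10.2.3) carries forward the mean observed on treatment, so it needs observed data.
- Within-group imputation (SAP 10.2.3) is under the same mITT rule.
- The off-treatment estimand MMRM (Protocol 7.4, SAP 10.5) uses windows that run past the treatment period for early stoppers. SAP 10.5.2 expects its population to be at least as large as mITT. It recovers early stoppers who reach 14 diary days in a window after stopping. It is fitted to observed data without reference-based imputation, so people who also stopped the diary are absent.

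**Step 3: reproduce the plan's figure.** Inputs from Protocol 7.6 and Table 7-1: 218 per arm, difference 1.5 days, SD 3.5 days, two-sided alpha 0.0167 per dose.

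Standard error = 3.5 x sqrt(2/218) = 0.335 days. Power by the normal approximation = 98.1%, and by the noncentral t = 98.1%. The stated 98% reproduces.

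**Step 4: size of the gap.** Let d be the share of each arm with no evaluable month. The documents give no value, so d is an assumption. If the excluded atogepant participants take the placebo profile, the expected difference is 1.5 x (1 - d) with n = 218. The mITT version keeps 1.5 with n = 218 x (1 - d). SD is held at 3.5.

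| Assumed d | Excluded per arm | Difference with them imputed (days) | Power with them imputed | Power in mITT |
|---|---|---|---|---|
| 1% | 2.2 | 1.485 | 97.9% | 98.0% |
| 2% | 4.4 | 1.470 | 97.7% | 97.9% |
| 3% | 6.5 | 1.455 | 97.4% | 97.8% |
| 5% | 10.9 | 1.425 | 96.8% | 97.6% |
| 10% | 21.8 | 1.350 | 94.9% | 96.8% |

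At d of 1-5% the shift is 1.5 x 0.01 = 0.015 to 1.5 x 0.05 = 0.075 days, about 4-22% of one standard error.

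**Step 5: tipping point.** The smallest difference significant at 0.0167 is about 0.80 days. Dilution alone reaches it at d = 1 - 0.80/1.5, about 47%.

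**The case against.** The strongest counter-argument is that copy-reference is a check on the MMRM. People with no post-baseline month contribute nothing to an observed-case MMRM. Holding the dataset fixed and changing only the missing-data assumption is a legitimate design, whereas widening the population changes two things at once. That stands as a reason to keep the mITT version as one run and to leave the primary alone. It does not defeat a run on the wider set, which asks a different and useful question.

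Several stronger readings are tempting, and the documents do not support them:

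- *That the plan would hide an imbalance in very early dropout.* SAP Section 7 tabulates ITT and mITT counts by arm, and discontinuations with reasons by arm. ITT minus mITT gives the numbers. Only the efficacy estimate is silent.
- *That everyone who stops in the first weeks is lost to the efficacy analyses.* Those with 14 diary days in a double-blind window are in mITT, and early stoppers are required to keep the diary through Visit 8 (Protocol 8.8), which feeds the off-treatment analysis.
- *That the earliest losses are mainly due to tolerability or lack of effect.* Protocol 8.8 lists both among the possible reasons for discontinuation and says nothing about their timing or frequency.

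There is also a limit on what can be seen. The copy-reference specification is not visible in SAP 10.2.3, and SAP Section 6 allows exceptions. The population is therefore inferred from the general rule. No exception is visible, and SAP Section 19 lists no changes from the protocol.

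**Conclusion.** The point holds as a minor gap. On the visible text, the copy-reference analysis covers only participants with at least one evaluable double-blind month, and those who stop both drug and diary before then enter no visible efficacy analysis.

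A reader might infer that the primary result is fragile or that the sensitivity analysis materially overstates robustness. The numbers do not support that. At an assumed early loss of 1-5% the planning difference would shrink by 0.015-0.075 days and power would stay at 96.8% or above. Even 10% leaves 94.9%. The direction in the drug's favour is an expectation that follows from imputing zero effect when the drug works. It need not hold in every realised dataset and is not evidence of bias.

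The conclusion rests on three assumptions: the mITT default applies to copy-reference, the early-loss rate lies in the range shown, and the planning difference and SD hold.

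**What to change.** First check the SAP text that is not visible. If it already names a wider population for copy-reference, nothing is needed. Otherwise:

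- Run copy-reference multiple imputation on all randomised participants with an evaluable baseline, in addition to or in place of the mITT version.
- For those with no evaluable month, impute all three months from the placebo distribution, given baseline and prior-exposure stratum.
- Report beside it the number excluded from mITT in each arm, which the SAP Section 7 counts already yield by subtraction.
- Leave the primary MMRM in mITT as planned.

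The cost is one sentence in the SAP and one population flag in an analysis already planned. The downside is a slightly less favourable sensitivity estimate.
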